Aim 2: Through an open label treatment study, we will define thiamine deficiency disorders (TDDs) as cases with low or “low normal” thiamine levels and symptoms of TD that improve with thiamine replenishment. Hypothesis 2: The current bioassays of thiamine do not accurately define TDDs and individuals with results the “low normal” range will show symptom improvement with thiamine replacement.

Aim 3: Utilizing a nested case control study design, determine if acute and chronic inflammatory conditions with elevated biomarkers of inflammation increase the risk of developing TDDs. Hypothesis 3: Acute and chronic forms of inflammation cause oxidative stress which increase basal requirements for thiamine as a metabolic cofactor and increase the risk of developing TDDs.

Study Population:

We anticipate 300 patients will be enrolled in this study with an age range of 18 and older. There will be no exclusions due to gender, race, age, or ethnicity. We will endeavor to include women and minorities to the extent possible based on the inpatient population which historically has been predominantly male (95%) and white (90%). All subjects recruited for this study will be Veterans admitted to inpatient units at VA Sierra Nevada Healthcare System hospital (single site recruitment). There will be no minor children participating. The health status will be compromised from mild to severe due to the nature of being hospitalized. We will not include adults unable to consent (those who are cognitively impaired with Impaired Decision-Making Capacity). We will not enroll pregnant women as we do not admit them to the VA hospital due to lack of maternity services.

Inclusion criteria:

- anyone age 18 or older requiring full hospital admission to the medical service.

Exclusion criteria:

- excess alcohol intake as defined by the National Institute of Alcohol Abuse and Alcoholism as more than 14 standard drinks per week for men less than age 65, or more than 7 drinks per week for women or men 65 years of age or older
- unable to consent due to impaired decision making capacity.
- veterans who live more than 75 miles from the study site as that would likely hinder their ability to attend follow up visit 3.
- Veterans who suffer from quadriplegia because they cannot participate in the physical assessments
- Veterans taking thiamine supplements

Vulnerable Populations:

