10.2 Visit 2 – second hospital encounter: Following stabilization of the acute medical condition(s) for which they presented, the Veteran (and caregiver if the Veteran agrees) will be interviewed and examined by the study's PI or trained advance care practitioner using a standardized checklist of signs and symptoms of TD. We will delay this portion of the assessment until the primary treating team affirms their acute condition has stabilized to avoid misclassification of symptoms from the acute illness with those of TDD. In most cases we anticipate this will occur just prior to hospital discharge. For Veterans with symptoms suggestive of TD, we will provide a prescription for thiamine replacement 100 mg orally daily for two weeks (see **Standardized physical examination and related data**).

Nutritional history: Study personnel will perform a dietary history to adequacy of thiamine intake, recent changes in appetite, food intake or any social or medical risk factors for malnutrition. We will review medical records for acute and chronic medical illnesses that may predispose to malnutrition.

Symptom and function survey: The patient interviews will include questions about the following: acute or worsening symptoms in the following categories: neuropsychiatric (including memory loss, personality or behavior change, psychosis, mood changes, seizures), polyneuropathy (to include muscle weakness, loss of deep tendon reflexes, neuropathic pain, or sensory loss), GI dysfunction (including dysphagia, anorexia, nausea, vomiting, gastroparesis, or constipation), and cardiovascular manifestations (such as palpitations, tachycardia, dyspnea, pulmonary or peripheral edema). We will review recent trends in ability to carry out Basic Activities of Daily Living (ADLs) and Instrumental Activities of Daily Living (IADLs). We will determine if there are symptoms of adult failure to thrive such as weight loss, decreased appetite, inactivity, poor nutrition, depression, loss of functional status as defined by loss of ability to do ADLs or IADLs. We will also ask about medication compliance with both prescribed and over the counter medications and supplements.

Standardized physical examination and related data: We will perform targeted exams for signs of TDDs including mental status exam using the Montreal Cognitive Assessment (MoCA); delirium screen using the 4AT

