10.3 Visit 3 – follow-up of symptomatic Veterans after empiric thiamine treatment. All Veterans with low biomarkers OR low normal biomarkers and clinical symptoms of TDDs that were initiated on replacement will be seen at a follow-up visit 3 after two weeks of thiamine replacement. We will repeat the symptom and function survey and repeat the standardized physical assessment. We will categorize changes in symptoms and signs as *no or minimal improvement, or noticeable improvement*. We will re-order thiamine biomarkers to assess for increases in levels. We will recommend continued dosing with thiamine 100 mg daily thereafter for any Veteran with improvement in their symptoms and update their medical record to include thiamine deficiency in their problem list. If a participant failed to complete the 2 weeks of replenishment, we will provide another 2-week course of replenishment and reschedule this visit.

Study Duration/ Study Timeline:

See Table 3. We expect visit 1 will not take substantial time for the Veteran. Visits 2 and 3 will take between 60 and 90 minutes each. For Veterans without symptoms of TD, their participation will be complete after visit 2, before discharge from the hospital. For Veterans with symptoms of TD their participation will be complete after taking thiamine for 2 weeks and attending visit 3. We anticipate the study will end 24 months.

Study Endpoints:

Our primary endpoint will be determining prevalence of TD in our Veteran population. We do not anticipate stopping the study before 300 Veterans are recruited. Thiamine supplements are very safe with few side effects, so we do not anticipate stopping early for safety concerns.

Study Locations:

The study will be conducted at the VA Sierra Nevada Healthcare System Hospital inpatient units at [name]. Follow up visits will occur on the ground floor of the hospital in the research department exam rooms.

International Research:

We will not be conducting this research in international locations.

Participant Compensation:

Those that agree to participate will be compensated \$30 for visits 1 and 2 and \$200 if they attend visit 3 after discharge.

Economic Burden to Participants:

Veterans will not incur any costs because of participating in this study. Those that attend the follow up visit will incur the cost of transportation, but this will be mitigated by the \$200 compensation.

Risk to Participants:

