Measurements: The **primary outcome** of this study is to measure the prevalence of TD as defined by abnormally low or low normal thiamine biomarkers combined with symptoms that respond to thiamine replenishment. **Secondary outcomes** will include describing demographic, clinical, and nutritional characteristics among those with and without TDDs. A TDD will be defined as an acute condition with symptoms that are known to be due to TD and that improve with adequate thiamine replenishment.

Statistical analysis/power calculations: Our primary endpoint is the prevalence of TDDs which we will compute as the proportion of TDD cases over the total number of subjects enrolled. Given the feasibility of this study and our patient population, we believe we can enroll and follow 300 subjects over a one-year enrollment period with an anticipated drop-out rate of 15%. Current best estimates for TD in similar populations are approximately 25%^{19,24,27}. Such an enrollment would provide us with a precision of TDD prevalence of +/- 5.4%. A sample size of 300 and estimated drop out of 15% leaving 255 subjects would provide us with 81% power to detect an 8% absolute difference from this expected prevalence. To explore differences in demographic, clinical, and nutritional characteristics among those with and without TDDs, continuous variables will be compared by T-test unless parametric assumptions are not met in which case a Kruskall-Wallis test will be used. Categorical variables will be evaluated through Chi-square or Fishers exact test depending on assumptions being met. We will estimate prevalence rate ratios for association factors. If the prevalence is achieved, we estimate that we would have adequate numbers to identify a range of different rates of exposure variables among TDD and non-TDD patients. For example, with 63 TDD and 192 non-TDD patients and a 10% rate of a given explanatory variable, we would have 80% power to detect prevalence rate ratios of ~2.5 and higher in bivariate analyses.

15.2 Open label treatment study to develop standardized case definitions of treatment responsive TDDs and correlate with thiamine biomarker levels to determine clinically relevant cut-points of those biomarkers.

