Measurements: The **primary outcome** of this arm is to determine if there are differences in markers of inflammation as evidenced by hs-CRP and fibrinogen between TDD and non-TDD hospitalized Veterans. Presence of inflammation will be defined as hs-CRP higher than upper limits of normal 0.75 milligrams/deciliter (mg/dL), or fibrinogen higher than the upper limits of normal 471 mg/dL. Individuals will also be considered to have inflammation if they are diagnosed with one of the AICs or CICs previously described.

Statistical analysis: The presence or absence of AICs and CICs among those with and without TD (defined as treatment responsive TD or abnormal thiamine levels based on clinical laboratory standards) will be evaluated by Chi-square or Fisher's exact test depending on assumptions being met. An assessment of total number of AICs and/or CICs between TD and non-TD patients will be assessed using the student's T-test or non-parametric methods depending on necessary assumptions being met. To evaluate if biomarkers of inflammation (hs-CRP and/or fibrinogen) are associated with presence or absence of TD we will compare levels between these two groups. If group sizes are large enough, we will attempt to develop exploratory multivariate models to identify AICs, CICs, and inflammation markers which are associated with TDD status. As no studies have reported on inflammatory markers, AICs, and CICs and thiamine deficiency, this is an exploratory aim for which we have no data to estimate a priori sample size requirements.

Resources Available

The VA hospital is a 64-bed general medical and surgical facility. There are typically 10 patients admitted to the hospital daily and we expect no trouble enrolling 300 patients in our study over 12 months. [name] will dedicate 3/8ths of her full-time employment with the VA managing this project. We will have a full-time research coordinator and a half time Health Systems Specialist (PA or ARNP) performing the day-to-day operations of the study. [name] will train both employees on the research purpose and protocol and assign duties as appropriate to their background and training in completion of the study. Veteran participants will be given a detailed description of their role in the research project and will be provided phone numbers to contact study personnel in the event of an adverse outcome or symptom. All medical and psychological care will be provided through the VA for adverse events.

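### Aim 3 compares inflammation between groups defined wholly or partly by uncontrolled symptom improvement, so any difference in natural improvement by inflammatory status biases the association, in a direction the documents do not settle

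*Combined protocol and SAP*

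**What the plan says.** Section 4.3 (nested case-control study) uses two case definitions.

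- Its Measurements paragraph makes the primary outcome "differences in markers of inflammation as evidenced by hs-CRP and fibrinogen between TDD and non-TDD hospitalized Veterans".
- Its Statistical analysis paragraph compares acute and chronic inflammatory conditions (AICs, CICs), their counts and the marker levels by TD status, "defined as treatment responsive TD or abnormal thiamine levels based on clinical laboratory standards".
- The same paragraph returns to TDD for its conditional "exploratory multivariate models to identify AICs, CICs, and inflammation markers which are associated with TDD status".

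Section 15.1 defines a TDD as "an acute condition with symptoms that are known to be due to TD and that improve with adequate thiamine replenishment". Aim 2 defines it as low or low-normal levels with "symptoms of TD that improve with thiamine replenishment".

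Under section 10.3, treated Veterans with low markers, or with low-normal markers and symptoms, "will be seen at a follow-up visit 3 after two weeks of thiamine replacement". Change is then graded in two categories: none or minimal, or noticeable. A Veteran who did not complete the course is offered another and the visit is rescheduled, so the interval can lengthen. The Informed Consent Process section says that there is no blinding and no placebo.

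The plan has one safeguard. Section 10.2 delays the symptom assessment until the treating team affirms that the acute condition is stable, "to avoid misclassification of symptoms from the acute illness with those of TDD". It expects this to fall, in most cases, just before discharge.

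**The concern.** The outcome in Aim 3 is in part a measure of getting better. The exposure (an AIC or CIC, or raised hs-CRP or fibrinogen) marks illnesses that have their own course of improvement. The symptoms counted in section 10.2, such as weakness, anorexia, nausea, dyspnea, edema and changes in mood or memory, are also symptoms of those illnesses, and the Background says that the two overlap. No symptomatic Veteran is left untreated for comparison, so improvement due to thiamine cannot be separated from ordinary convalescence.

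If convalescence differs by inflammatory status, misclassification of the outcome is tied to the exposure. Such differential misclassification can produce an association where none exists, or hide a real one. Hypothesis 3 is a causal statement about TDD risk and would be judged on this comparison. Correcting the overall TDD prevalence would not repair it, because the error lies in the contrast between the groups.

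**Working it through.** **The plan's own figure.** Aim 3 states no sample size or power. The nearest figure is in section 15.1: 63 TDD v 192 non-TDD, 10% exposure, prevalence rate ratio about 2.5, 80% power. With 25% v 10%, two-sided 0.05 and no continuity correction:

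- SE under the null = √[p(1−p)(1/63 + 1/192)], with p = (63×0.25 + 192×0.10)/255 = 0.137, giving 0.0499.
- SE under the alternative = √(0.25×0.75/63 + 0.10×0.90/192) = 0.0587.
- Power = Φ[(0.15 − 1.96×0.0499)/0.0587] = 81%.

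The stated 80% reproduces. It assumes that case status is classified without reference to exposure.

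**Bias illustration.** From the documents: 255 Veterans after 15% dropout, split here as 127 inflamed and 128 not. Assumed, not in the documents: 15% low and 30% low-normal levels in both groups, 70% symptomatic, no thiamine effect, and two-week improvement r that may differ by group.

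- TDD = (0.15 + 0.30) × 0.70 × r = 0.315r.
- TD under the 4.3 *or* rule, with a marker required for response = 0.15 + 0.30 × 0.70 × r = 0.15 + 0.21r.
- Chance of p<0.05 = Φ[(|difference| − 1.96·SE₀)/SE₁], where SE₀ and SE₁ are the standard errors under the null and the alternative, for 127 v 128.

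| r, inflamed v not | TDD | Ratio | Chance p<0.05 | TD (*or* rule) | Ratio | Chance p<0.05 |
|---|---|---|---|---|---|---|
| 60% v 40% | 18.9% v 12.6% | 1.50 | 28% | 27.6% v 23.4% | 1.18 | 12% |
| 60% v 30% | 18.9% v 9.45% | 2.00 | 58% | 27.6% v 21.3% | 1.30 | 21% |
| 40% v 60% | 12.6% v 18.9% | 0.67 | 28% | 23.4% v 27.6% | 0.85 | 12% |
| equal | equal | 1.00 | 5% | equal | 1.00 | 5% |

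For the first TDD row: SE₀ = 0.0456, SE₁ = 0.0455, Φ[(0.063 − 0.0894)/0.0455] = Φ(−0.58) = 28%. The 5% in the last row is the nominal two-sided level.

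**Sensitivity to the assumed rates.** A second set was simulated with N = 255: 50% symptomatic with low or low-normal levels, 14% of all Veterans abnormally low (within that 50%), and half of Veterans inflamed. At 60% v 40%:

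- TDD is 0.50×0.60 = 30% v 0.50×0.40 = 20%, a ratio of 1.50, with 46% of tests significant.
- TD under the *or* rule is 0.14 + 0.36×0.60 = 35.6% v 0.14 + 0.36×0.40 = 28.4%, a ratio of 1.25, with 23% significant.
- At 55% v 45%, the TDD ratio is 1.22, with 15% significant.
- With case status defined by the abnormal baseline level alone, about 5% of tests were significant for every improvement pattern tried. That follows from simulating levels as independent of inflammation. It shows only that differential improvement cannot enter that outcome.

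**The case against.** The strongest reply has four parts.

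1. *The plan anticipated the problem.* Section 10.2 waits for stability. This stands as a mitigation. But stable enough for discharge is not recovered, the following two weeks are convalescence, and no analysis adjusts for it. How much bias remains is unknown.

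2. *Most of the definite tests use TD, not TDD.* This is correct. TDD appears only in the primary-outcome sentence and in models that depend on group size. A reader might infer that every Aim 3 test requires recovery within two weeks. The documents do not support that: an abnormal level alone makes a TD case, the criterion is noticeable improvement, and the interval can lengthen. The bias under TD is smaller, but not zero.

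3. *The direction is assumed.* This also stands. A reader might infer that Hypothesis 3 will be falsely supported because acutely inflamed Veterans recover anyway. No passage says that inflamed Veterans improve more often, and Aim 3 pools acute with chronic conditions, which may improve less. The bias could equally mask an association.

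4. *The aim is exploratory, and Hypothesis 3 concerns TDDs rather than levels.* Section 4.3 does call the aim exploratory, which limits the priority. The Background says that the assay reference ranges are not validated in clinical TDDs, and Hypothesis 2 doubts that the assays define TDDs. That is a fair reason not to replace the TDD comparison outright. It is not a reason to leave it as the only primary comparison.

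A larger figure is also tempting. If treatment response needed no marker, TD would be 0.15 + 0.85×0.70×r. At 60% v 30% that is 50.7% v 32.9%, a ratio of 1.54 and an 83% chance of p<0.05. Aim 2, section 10.3 and the primary outcome in 15.1 tie response to low or low-normal markers, so I do not rely on that reading.

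**Conclusion.** The point holds in conditional form. The Aim 3 primary outcome and multivariate models depend wholly, and the remaining tests partly, on improvement that has no control. Any difference in natural improvement by inflammatory status then biases the result.

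In the main illustration, a gap of 20 percentage points moves the TDD ratio to 1.5 or 0.67 and raises the chance of a spurious p<0.05 from 5% to 28%. For TD with a marker required, gaps of 20 to 30 points give ratios of 1.18 to 1.30 and a 12% to 21% chance. Every rate behind these numbers is an assumption; only the 255 comes from the plan. With equal improvement there is no bias.

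The switch between TD and TDD within 4.3 is a defect on the face of the text and needs no assumption. This is worth correcting before analysis, in proportion to an exploratory aim.

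**What to change.** In section 4.3:

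- Use TD and TDD consistently, and do not pool marker-defined and response-defined cases by *or*.
- (a) As a co-primary or key analysis, estimate the association of hs-CRP, fibrinogen, AIC and CIC (acute and chronic kept separate) with the Visit 1 levels of each thiamine biomarker, continuous and below v above the laboratory limit, in all Veterans with a valid Visit 1 sample.
- (b) Report the response-defined TDD comparison separately, among symptomatic treated Veterans, stating that improvement is uncontrolled.
- Reconcile 4.3 with Table 3 and the laboratory list in 10.1. Neither names hs-CRP or fibrinogen, so their collection and timing are undefined. List the AICs and CICs, which 4.3 treats as already described but which I could not find in the text available.

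**Cost.** No new visits, and the thiamine samples are already planned. Wording in 4.3 alone is not enough, however, if hs-CRP and fibrinogen are not collected in every participant. Analysis (a) answers a question about thiamine level rather than clinical TDD, with reference limits not validated in clinical TDDs. It does not depend on Visit 3, but a gain in numbers over 255 is not established: the plan does not attribute its dropout to Visit 3, and 10.1 allows for lost thiamine results.
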